- Safety including acute GVHD grades III-IV within 42 days of the last dose of VSTs or grades 3-5 non-hematological adverse events within 28 days of the last VST dose and that are not due to the pre-existing infection or the original malignancy or pre-existing co-morbidities as defined by the NCI Common Terminology Criteria for Adverse Events (CTCAE), Version 4.X.

Secondary Endpoints

- Antiviral responses 42 days after the first dose of VSTs
- Effects of partially HLA-matched VSTs on viral loads
- Persistence of partially HLA-matched VSTs and effects on clinical signs/symptoms
- Reconstitution of antiviral immunity at 1, 2, 3, 4,6 weeks and 3 months
- Viral reactivations within 12 months
- Secondary graft failure at 30 days
- Chronic GVHD at 3 months, 6 months and 12 months
- Clinical response to VST infusions at 6 weeks and 3 months
- Effects of HLA matching
- Effects of choosing a line with confirmed antiviral activity through one or more shared alleles
- Overall survival at 3 months, 6 months and 12 months

CHARMS Protocol v1.0 (10.30.13)	Version 5.0 (10.6.15)
Version 2.0 (12.09.13)	Version 6.0 (08.29.16)
Version 2.1 (03.07.14)	Version 7.0 (04.26.17)
Version 3.0 (06.17.14)	Version 8.0 (05.24.17)
Version 4.0 (11.06.14)	Version 9.0 (08.10.17)

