1.8.5.2 Clinical activity of donor-derived multivirus-directed VSTs

We evaluated the clinical utility of multivirus VSTs in recipients of matched related, matched unrelated, or haploidentical donor transplants. To date, 35 clinical-grade multivirus-directed VSTs have been generated from donor PBMCs. These lines were polyclonal, comprising both CD4+ (57±5%) and CD8+ (35±5%) cells and retained expression of the memory markers CD45RO+CD62L+ (58±8%). Their specificity was dependent on the prior viral exposure of the cell donor; 32/35 lines had activity against Adv, 20/35 against CMV, 26/35 against EBV, 18/35 against BK and 21/35 against HHV-6. None of the lines reacted against recipient PHA blasts – indicating lack of alloreactive potential in these rapidly generated lines.

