2.2 Rationale for Study Design

The primary purpose of this pilot study is to assess the safety of administering partially HLA-matched VSTs in transplant patients with BK virus, HHV6, EBV, CMV, and/or adenovirus infection. We have elected to use a dose of 2×10^7 VSTs/m², which has been shown to be safe and have clinical activity in a Phase I study using the same T cell product in the donor-specific setting. Because the persistence of adoptively transferred cells may be shorter using a partially HLA-matched banked VST product, we have included an option of administering additional doses in subjects that have a partial response after one dose.

It is unclear what degree of matching will be needed for clinical activity so we propose to allow infusion of lines that match at only one antigen, with expected antiviral activity against the infecting

CHARMS Protocol v1.0 (10.30.13)	Version 5.0 (10.6.15)
Version 2.0 (12.09.13)	Version 6.0 (08.29.16)
Version 2.1 (03.07.14)	Version 7.0 (04.26.17)
Version 3.0 (06.17.14)	Version 8.0 (05.24.17)
Version 4.0 (11.06.14)	Version 9.0 (08.10.17)

virus through this single shared allele, although preference will be given to lines matching at the most loci where anti-viral activity through a shared allele has been confirmed.

For CMV infection, standard therapy is well defined as antiviral agents with ganciclovir being the agent of choice and foscarnet or cidofovir being effective second line agents. For EBV infection, rituximab is the current treatment of choice for patients with CD20+ lymphoma. For patients with CD20- tumors there is no clear standard of therapy although most physicians would likely administer chemotherapy. There is also no clear standard therapy for adenovirus or BK virus, although there are reports of cidofovir having activity. We have therefore chosen to use cidofovir as standard therapy for both these infections although this requirement would be waived if the subject could not tolerate this agent due to nephrotoxicity. Ganciclovir, cidofovir, and foscarnet have variable in vitro activity against HHV-6, and may have a role in treating HHV-6-associated disease. Hence standard therapy will include treatment with one or more of these agents.

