2.4 Treatment Plan

2.4.1 VST Line selection and availability

2.4.1.1 VST Lines selection

We will use multivirus-specific VSTs, generated initially for use on our donor-specific study. The lines were generated using a rapid protocol whereby clinical grade pepmixes spanning immunogenic antigens from each of our target viruses are used to directly stimulate PBMCs, followed by expansion in the presence of growth promoting cytokines and the G-Rex culture device optimized for T cell expansion. Donor-specific VST lines generated according to this protocol were previously found to be safe and effective in a Phase I clinical trial as discussed.

To initiate the multivirus-specific VSTs 15×10^6 PBMCs were pulsed with a master mix of pepmixes spanning Adv (Hexon and Penton), CMV (IE1 and pp65), EBV (LMP2, EBNA1, BZLF1), BK virus

CHARMS Protocol v1.0 (10.30.13)	Version 5.0 (10.6.15)
Version 2.0 (12.09.13)	Version 6.0 (08.29.16)
Version 2.1 (03.07.14)	Version 7.0 (04.26.17)
Version 3.0 (06.17.14)	Version 8.0 (05.24.17)
Version 4.0 (11.06.14)	Version 9.0 (08.10.17)

(VP1 and large T) and HHV6 (U90, U11 and U14). After 30mins the cells/pepmix combination was transferred directly to the G-Rex culture device. The VST media was supplemented with the cytokines IL7 and IL4 (10ng/ml and 400U/ml, respectively) in order to inhibit apoptosis and promote expansion of multivirus-specific T cells.

The VST lines were checked for identity, phenotype and sterility, and cryopreserved prior to administration according to our SOP. To test the functional antigen specificity of the VST we will use individual pepmixes spanning each of the viral antigens used in the initial stimulation as a stimulus in IFN γ ELIspot. Epitope mapping will be performed using known HLA epitope peptides or peptide mini-pools to identify novel immunogenic epitope peptides within our target antigens.

Products that meet study specific release criteria, as detailed on the CofA, will be infused as per Section 2.4.2.

If a positive sterility testing result is reported after the product is infused, the FDA and other relevant parties will be notified as per our manufacturing SOP B01.03.XX (Product Quality Assurance Program and Release and Return of Clinical GMP/GTP Products) and clinical research SOP J02.06.XX (Serious Adverse Experience and Unanticipated Problem Reporting). Management of such a situation is further described in our SOP F05.09.XX (Management of Culture Positive Cell Therapy Products).

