2.4.1.4 Criteria for Selection of VST Line

In general preference will be assigned to the infusion of a line with confirmed virus-specific activity against the infecting virus through a shared HLA allele rather than the overall level of HLA match. For example for a patient with an adenovirus infection a line that matches at 2 loci but that has recognition of adenovirus mediated through those antigens would be preferable to a line matched at 3 loci but with no demonstrated activity against adenovirus. Patients with a partial response are eligible to receive up to 4 additional doses.

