5.2 Sample Size Determination and Design Characteristics

Frist, the study will conduct a single arm pilot study using a phase IIa design. Simon's two-stage Minimax design⁶⁰ will be used to for the single-arm pilot study. Under the null hypothesis that the VST is not active, the data from previous trials suggest that the true response rate is 20% in anti-viral activity, where a positive response is defined as the viral load reduction to the normal level for at least one of the 5 virus types (CMV, EBV, adenovirus, BK virus and HHV6) within 42 days following the initial treatment of VST.

Allowing a 5% type-I error and 90% power, the null hypothesis will be tested against a one-sided alternative that the true response rate is 40%. The maximum size is 45 eligible patients, defined as the patients who receive the VST infusion and who can finish the 42 days follow-up. We anticipate that most patients will finish the follow up and will allow a 10% drop out rate. Therefore, the maximum sample size is 50.

The phase IIa trial operates in two stages, where the first stage recruits 24 patients. The trial pauses at the end of the first stage to make the decision on whether to stop the trial early due to lack of enough efficacy for treating viral infection, according to the rule as follows. Of the 24 patients at the first stage, if 5 or fewer positive responses are observed, then the study will be stopped. Otherwise, 21 additional patients will be accrued to reach the goal of 45 accruals. At the end of the trial, the null hypothesis will be rejected, if 14 or more positive responses are observed in among the 45 patients. This design has 65.6% chance to stop early when the true response rate is 20%.

After the phase IIa trial suggests excellent clinical responses that warrant further investigation, the study will be expanded to recruit 30 additional patients to evaluate the viral reduction based HLA matching. We hypothesize the viral reduction among the low HLA matching group (1/8, 2/8, or 3/8 HLA matching) is not worse than the high HLA matching group (4/8, 5/8, 6/8, 7/8, or 8/8).

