The sample size is calculated based on non-inferiority trial for comparing two-sample means. Based on the preliminary data, the standard deviation of viral reduction is about 18. We assume that the viral reduction in the low HLA matching group is not inferior to the high HLA matching group when the difference in the viral reduction between the two groups is no less than -10 (non-inferiority margin). Preliminary data suggest that the ratio of sample size between the low and high HLA matching groups is 5 to 7. A sample size of 30 patients with low HLA matching and 42 with high HLA match (total 72) would have at least 85% power to test the non-inferiority hypothesis with 2-side 5% alpha level. Assuming 10% of patients to be lost to follow-up, then the study will recruit up to a total of 80 patients.

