5.4 Data Analysis

Safety and toxicity outcomes including adverse events, GvHD, clinical signs of viral infections, secondary graft failure and laboratory measurements will be summarized using descriptive statistics (frequency table, means, standard deviations, medians and ranges). Toxicity information including the type, severity, time of onset, time of resolution, and the probable association with the study regimen will be tabulated and summarized.

Response rate including complete response, partial response and mixed response will be summarized as frequency table. The response rate with 95% CI will be reported. Reconstitution of antiviral immunity using multimer analysis and ELISpot assays will also be summarized using descriptive statistics at each time point. Pairwise comparisons will be performed to compare changes of these immunological parameters from VST infusion to each time point of post-infusion measurements using paired t-tests or Wilcoxon signed-ranks tests. The normality assumption will

CHARMS Protocol v1.0 (10.30.13)	Version 5.0 (10.6.15)
Version 2.0 (12.09.13)	Version 6.0 (08.29.16)
Version 2.1 (03.07.14)	Version 7.0 (04.26.17)
Version 3.0 (06.17.14)	Version 8.0 (05.24.17)
Version 4.0 (11.06.14)	Version 9.0 (08.10.17)

be assessed and transformations to achieve approximate normality will be carried out if necessary. Overall survival post VST infusion will be analyzed by the Kaplan-Meier method.

Viral load reduction will be compared between the low and high HLA using the two-sample t-test. Additionally, Viral load levels will be correlated with immunological parameters using correlation coefficients. Longitudinal analysis is employed to model repeatedly-measured immunologic parameters. This will allow us to model patterns of immune response per patient while allowing for varying intercepts and slopes for a patient. Viral load levels will be correlated with immunological parameters using correlation coefficients. These modeling strategies will be considered exploratory in nature due to the limited patient numbers in this initial trial.

Overall survival since allogeneic hematopoietic stem cell transplant will be analyzed using the Kaplan-Meier method. Cumulative incidences to the time of complete/partial resolution of viral infection and viral load reduction, considering death a competing event, will be analyzed in univariate and multivariate model using the Fine and Gray method.

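### Section 5.4 compares viral load reduction by HLA match with an unadjusted t-test, although line selection, not randomisation, forms the groups and can link match level to virus type

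*Combined protocol and SAP*

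**What the plan says.** Section 5.4 gives one method for the HLA comparison: "Viral load reduction will be compared between the low and high HLA using the two-sample t-test". It names no covariate, stratum or matching.

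Section 5.2 supplies the hypothesis, that "the viral reduction among the low HLA matching group (1/8, 2/8, or 3/8 HLA matching) is not worse than the high HLA matching group", with a margin of -10, an SD of about 18, and 30 low-match and 42 high-match patients. The 5:7 ratio comes from preliminary data; it is not an allocation. Section 5.1 describes a single-arm study and gives the role of HLA matching as the reason for the 30-patient expansion.

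Match level arises from line selection. Section 2.4.1.4 states that "preference will be assigned to the infusion of a line with confirmed virus-specific activity against the infecting virus through a shared HLA allele", ahead of overall match. Section 2.2 adds that "preference will be given to lines matching at the most loci where anti-viral activity through a shared allele has been confirmed". Section 1.8.5.2 reports, for the donor-derived lines, that "32/35 lines had activity against Adv, 20/35 against CMV, 26/35 against EBV, 18/35 against BK and 21/35 against HHV-6", and Section 2.4.1.1 says: "We will use multivirus-specific VSTs, generated initially for use on our donor-specific study". The Study Schema lists, as a secondary endpoint separate from HLA matching, "Effects of choosing a line with confirmed antiviral activity through one or more shared alleles".

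**The concern.** If lines active against a virus are scarcer, the best active line will tend to match the patient less well. A low-match group could then hold more BK patients and fewer adenovirus patients than a high-match group. If viral reduction also differs by virus, the raw difference mixes the effect of match level with that of virus type, and low-match lines could look better or worse than they are.

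This matters because the comparison has its own hypothesis, margin and stated power, and sets the maximum of 80 patients. The only multivariable models in Section 5.4 with a viral outcome are the Fine and Gray models. They analyse time to resolution or reduction and name no covariates.

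**Working it through.** **Inputs.** From Section 5.2: SD 18, margin -10, 30 low and 42 high, ratio 5:7, two-sided 5%, stated power at least 85%. From Section 1.8.5.2: active lines out of 35. From Section 1.10: response of 77.8% for adenovirus, 73.9% for CMV and 66.7% for EBV in the earlier third-party study. All else is marked as assumed.

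**1. The plan's own figure.** SE = 18 × sqrt(1/30 + 1/42) = 4.303. At true equality and two-sided 5%, power is 64.2% (normal) or 63.0% (t, 70 df). The stated 85% appears only at one-sided 10% (85.1%). That is a separate matter, but it makes 63% the baseline here.

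**2. Margin rule without confounding.** Half-width = 1.994 × 4.303 = 8.58. Non-inferiority needs an observed difference above -10 + 8.58 = -1.42. False non-inferiority at a true -10 is 2.5%.

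**3. How far line selection could unbalance virus type.** Assumptions: the best-matched active line is infused, lines are independent, the five viruses are equally common, and whole-line activity stands in for allele-confirmed activity. Then P(low | virus) = (1 - h)^n, where n is the number of active lines and h the chance that a line is a high match. Setting the mean to 5/12 gives h = 0.0374.

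| Virus | n | P(low) | Share of low | Share of high | Difference |
|---|---|---|---|---|---|
| Adenovirus | 32 | 0.295 | 0.142 | 0.242 | -0.100 |
| CMV | 20 | 0.466 | 0.224 | 0.183 | +0.041 |
| EBV | 26 | 0.371 | 0.178 | 0.216 | -0.038 |
| BK | 18 | 0.503 | 0.241 | 0.170 | +0.071 |
| HHV6 | 21 | 0.449 | 0.215 | 0.189 | +0.026 |

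Sum of positive differences: 0.041 + 0.071 + 0.026 = 0.138, about 14 points.

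**4. Shift under an assumed gap.** Suppose mean reduction differs by 9 to 18 units (half to one SD, assumed) between CMV, BK and HHV6 on one side and adenovirus and EBV on the other. The shift is 0.138 × 9 = 1.2 to 0.138 × 18 = 2.5 units.

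- In favour of low match: false non-inferiority at a true -10 is 4.7% to 8.2%.
- Against low match: the chance of showing non-inferiority at true equality is 52% to 41%.

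**5. Shift using the documents' by-virus rates.** Take the Section 1.10 rates as proxy units and let BK and HHV6 lie between 66.7 and 77.8 (both assumed). Shift = -0.100 × 77.8 + 0.041 × 73.9 - 0.038 × 66.7 + 0.071 × BK + 0.026 × HHV6. With unrounded differences this is -0.8 (both 66.7) to +0.3 (both 77.8). False non-inferiority is then 1.6% to 2.9%, and the chance at true equality 56% to 65%.

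**6. What adjustment does.** In a simulation (40,000 runs per cell; group, load and four virus indicators; load unrelated to outcome), the step 4 shifts in favour of low match gave false non-inferiority of 4.7% and 8.3% unadjusted against 2.5% and 2.4% adjusted. With no imbalance and uninformative covariates, the chance at true equality was 63% unadjusted and 60% adjusted.

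**The case against.** The strongest reply is that confounding by virus type may be small.

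- Section 2.3.4.1 adds a second source of lines, made for third-party use, some from donors already known to have broad antiviral reactivity. In the step 3 model, adding 10 to 35 lines active against all five viruses (an assumed number) cuts the imbalance from 13.8 points to between 9.8 and 5.7.
- In the earlier study, response differed by at most 77.8 - 66.7 = 11.1 points. Adenovirus and EBV, the highest and lowest, fall in the same set of step 4, so their effects partly cancel.
- In step 3, virus type explains only about 2% of the variation in group membership.

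All of this stands, and it limits the size that can be claimed. It does not remove the mechanism, and the earlier study gives nothing on BK or HHV6.

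Two further replies stand only in part. Section 5.4 calls its modelling strategies exploratory, but that sentence follows the correlation and longitudinal models, whereas the HLA comparison has a margin and a power statement. The Fine and Gray models allow several covariates, but they answer a time-to-event question.

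A reader might infer that the main analysis must also adjust for confirmed activity. The documents do not support that: such activity works through a shared allele and is partly a consequence of matching, so adjusting for it changes the question.

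**Conclusion.** The defect holds: an unadjusted test is planned for a non-randomised comparison whose groups can differ in virus type through the protocol's own selection rule. The change should be made. HLA effects are a secondary endpoint in a pilot study, so it is not a condition for the trial to proceed. Confidence is high for the defect and low to moderate for its size.

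The size is illustrative. The 4.7%-8.2% and 52%-41% figures rest on the assumed 9 to 18 unit gap, with every imbalance lined up in one direction. The documents' own response rates suggest a shift near zero for the viruses they cover.

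Three stronger readings are tempting and not supported:

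- *The comparison is biased towards non-inferiority.* No table crosses match level with virus, so neither direction nor size is known.
- *Match level is tied to pre-infusion load.* The documents do not say so; load belongs in the model because the outcome is a change from it.
- *The t-test ignores the margin.* Section 5.2 already implies a test against -10; Section 5.4 need only say so.

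**What to change.** Replace the t-test sentence in Section 5.4 with:

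> The main HLA comparison is a linear regression of viral load reduction at day 42 after the first infusion on match group of the first infused line (low 1/8-3/8, high 4/8-8/8), adjusted for virus type (sparse types pooled) and pre-infusion load of the treated virus. Non-inferiority is concluded only if the lower limit of the two-sided 95% CI for low minus high is above -10. The estimand is the total effect of match level, so confirmed activity through a shared allele is added only in a sensitivity analysis. The unadjusted t-test interval against -10 is reported as a second sensitivity analysis. Balance of virus type, pre-infusion load and confirmed activity is tabulated by group, and the result is described as a non-randomised comparison.

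The sponsor should also state the unit of the SD and margin, which Section 5.2 does not give, and how a patient treated for several viruses is counted. Day 42 should run from the first infusion whether or not more doses follow. Section 2.4.2.5 allows repeat doses at day 28 after an incomplete response, so ending assessment at a second dose would make its timing depend on outcome.

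Cost: SAP text, a record of confirmed activity for the infused line, and modest programming. Pre-infusion loads are already collected (Section 4.2.2). The model uses up to 5 covariate degrees of freedom in about 72 patients and costs about 3 points of power if the covariates are uninformative (60% against 63%). Unmeasured confounding remains.

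### Section 5.4 gives no null hypothesis, confidence limit or decision rule for the HLA non-inferiority question that section 5.2 defines and sizes

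*Combined protocol and SAP*

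**What the plan says.** Section 5.2 states the hypothesis for the 30-patient expansion: viral reduction in the low-match group (1/8 to 3/8) "is not worse than the high HLA matching group" (4/8 to 8/8). It goes on: "The sample size is calculated based on non-inferiority trial for comparing two-sample means". The criterion is that low match counts as non-inferior when "the difference in the viral reduction between the two groups is no less than -10 (non-inferiority margin"). The level is two-sided 5% and the claimed power is at least 85%.

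Section 5.4 gives the analysis in one sentence: "Viral load reduction will be compared between the low and high HLA using the two-sample t-test". It does not refer back to the margin. The only confidence interval named in 5.4 is the one for the response rate. No other section gives a rule for concluding non-inferiority.

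**The concern.** A two-sample t-test described simply as comparing two groups is normally understood as a test of no difference. The null of a non-inferiority test is that low match is worse by at least the margin. The two tests can disagree in either direction. A non-significant difference does not show non-inferiority, and a difference significantly against low match can still lie within the margin. As written, the analysis does not use the margin that set the sample size.

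The expansion from 50 to 80 patients is justified by this comparison, and section 2.2 says the degree of matching needed for activity is unclear. With the null and the rule unwritten, the choice between a test of no difference and a test against -10 stays open until the data are seen. That choice determines how often a true deficit at the margin would be reported as acceptable.

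**Working it through.** **Inputs, all from 5.2.** For the SD, "the standard deviation of viral reduction is about 18" (no unit given). The margin is -10 for low minus high (no unit given). On allocation, "the ratio of sample size between the low and high HLA matching groups is 5 to 7". On size, "A sample size of 30 patients with low HLA matching and 42 with high HLA match (total 72"). The level is two-sided 5%, which is one-sided 2.5% for non-inferiority. The true difference behind the power figure is not stated; 0 is assumed here.

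**Standard error.** SE = 18 × √(1/30 + 1/42) = 18 × 0.2390 = 4.303. Degrees of freedom are 30 + 42 − 2 = 70, and the critical t is 1.994. The margin in SE units is 10 / 4.303 = 2.324.

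**The plan's own figures first.** Dropout reproduces: 72 / 0.9 = 80. The power does not. Power at a true difference of 0 is Φ(2.324 − z):

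| Level | Power (normal) | Power (noncentral t) |
|---|---|---|
| one-sided 2.5% (two-sided 5%, as stated) | Φ(0.364) = 64.2% | 63.0% |
| one-sided 5% | Φ(0.679) = 75.1% | 74.4% |
| one-sided 10% | Φ(1.042) = 85.1% | 84.8% |

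The claimed 85% appears only at one-sided 10%, where the normal-approximation sample-size formula returns exactly 42 + 30 = 72. At the stated level, 85% with 72 patients would need an SD near 14.0, or a true advantage for low match of about 2.9.

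**How the two readings differ.** The half-width of the 95% CI is about 1.994 × 4.303 = 8.58 when the observed SD is 18.
- The test of no difference is non-significant when the observed difference lies between about -8.58 and +8.58.
- The margin test succeeds when the lower limit exceeds -10, that is, when the observed difference exceeds about -10 + 8.58 = -1.42.

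So an observed difference between about -8.58 and -1.42 is non-significant, yet non-inferiority has not been shown.

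**Error at a true difference of -10.**
- Probability of a non-significant t-test: 37.0% by noncentral t, 37.1% in a simulation of 400,000 trials, and 1 − Φ(0.364) = 35.8% by normal approximation.
- Probability that the lower 95% limit exceeds -10: 2.5% by construction, 2.4% in the simulation.

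**Sensitivity.** If all 80 patients were evaluable at 5:7 (33.3 and 46.7), SE = 18 × √(1/33.3 + 1/46.7) = 4.08. The non-significant share at -10 is then about 31% (normal approximation).

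**The case against.** The strongest reply is that 5.4 names a test but no null. The same t statistic, shifted by the margin, is the standard non-inferiority test for two means, and 5.2 already supplies the hypothesis, the margin and the level. Read together, the sections could mean a t-test against -10. This stands. The defect is an unstated null and decision rule, and the sections do not prove that the wrong analysis is planned.

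A reader might infer that the plan will treat p > 0.05 as proof that low match is not worse, and so will license poorly matched lines. The documents do not support that. No section says how a non-significant result will be read. Sections 2.2 and 2.4.1.4 already allow lines matched at one antigen and rank confirmed antiviral activity through a shared allele above overall match, so line selection does not wait on this test.

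A reader might also infer that the analysis as written can never establish non-inferiority. That goes too far: the t procedure yields the difference and its standard error, from which the limit to set against -10 follows.

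Nor do true differences of -5 or 0 show a false conclusion, because both lie inside the plan's margin. At 0, about 34% of trials are non-significant without showing non-inferiority. That reflects limited precision with 72 patients.

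Finally, HLA matching is one of many secondary endpoints in a single-arm pilot whose primary objectives are feasibility and safety. This lowers the priority but does not remove the gap. Section 5.4 calls its modelling exploratory, yet 5.2 gives this comparison a formal hypothesis, margin, level and power.

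**Conclusion.** The concern holds as a gap between the stated hypothesis and the stated analysis. Section 5.2 asks a non-inferiority question. Section 5.4 names a test that, in its usual meaning, does not answer it, and gives no rule that would. Depending on the unwritten choice, the chance of wrongly accepting low match when it is worse by the full margin is 2.5% (comparison with -10) or about 37% (non-significance read as not worse). The 37% is conditional on that reading and on 30 versus 42 evaluable patients with SD 18; it is not an error rate the plan prescribes.

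A related shortfall must be disclosed with the fix. At the stated two-sided 5% and an assumed true difference of 0, the margin test has about 63% power, not at least 85%. Severity: should fix.

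**What to change.** Replace the sentence in 5.4 with:

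> The mean difference in viral load reduction (low minus high) will be reported with its two-sided 95% CI from the two-sample t procedure. Non-inferiority is concluded only if the lower limit is above -10. Otherwise non-inferiority has not been shown, whatever the p-value for a difference.

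This uses the plan's own margin and level and needs no new data. The unit of the margin should be stated at the same place, so that the difference and the -10 are on one scale.

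The cost is candour about power. Section 5.2 should restate the figure as about 63% at a true difference of 0, or give the inputs that yield 85%. Reaching 85% at two-sided 5% with SD 18 and a true difference of 0 would take 50 + 70 = 120 evaluable patients, which is 120 / 0.9 = 133.3, so 134 recruited with 10% loss. If the sponsor keeps 80, the text should say that an inconclusive result is a realistic outcome even if the groups are equal.
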